#### **10.4.4 Concomitant medication**

Concomitant medication will be coded using the WHO drug dictionary (version is documented in the DMP). Concomitant medication will be listed.

#### **10.4.5 Clinical laboratory parameters**

All clinical chemistry and hematology data will be summarized by treatment and time point together with change from baseline, where baseline is defined as Day 1 predose, and listed. Urinalysis data will be listed. Additionally, clinical chemistry, hematology and urinalysis data outside the reference ranges will be listed and flagged on individual participant data listings.

Values recorded as  $< x$ ,  $\leq x$ ,  $> x$ , or  $\geq x$  will be displayed in the listings as recorded. For the calculation of summary statistics,  $< x$  and  $\leq x$  values will be set to  $0.5 \times x$ , whereas  $> x$  and  $\geq x$  values will be set to  $1.1 \times x$ .

#### **10.4.6 Vital signs**

Vital signs data will be summarized by treatment and time point together with changes from baseline, where baseline is defined as the Day 1 predose assessment. Figures of mean vital signs and mean changes from baseline profiles will be presented by treatment.

Values for individual participants will be listed.

Change from baseline in supine blood pressure and pulse rate will be analyzed using a mixed model for repeated measures. The model will include baseline (Day 1 predose) as a covariate, treatment, timepoint and the treatment-by-timepoint interaction as fixed effects, and participant as a random effect. An unstructured covariance structure will be used to model the covariance

between a participant's multiple observations, with an alternative structure to be used if the model fails to converge. Follow-up data will not be included in the model.

One model including all treatments (A1, A2, A3, B1 and B2) will be used to present comparisons of each test formulation versus the reference formulation at each post-dose timepoint. The difference in least squares means, along with the 90% confidence interval, will be reported.

Example SAS code:

```
proc mixed data=xxxx;
  by param;
  class treat time subjid;
  model chg = base treat time treat*time / residual ddfm=kr2;
  repeated time / subject=subjid type=un;
  lsmeans treat*time / cl pdiff alpha=0.1;
  ods output lsmeans=lsm diff=diff;
run;
```

#### **10.4.7 Electrocardiogram (ECG)**

ECGs will be performed for safety monitoring purposes only and will not be presented. Any clinically significant findings from ECGs will be reported as an AE.

#### **10.4.8 Hepatic Monitoring**

If a participant experiences elevated laboratory parameters, as detailed in Section 8.2.5.1 of the protocol, additional tests will be performed to confirm the abnormality. Additional safety data may be collected if required, as defined in the protocol. Where applicable, the following will be presented.

The participants' liver disease history and associated person liver disease history data will be listed. Use of acetaminophen during the study, which has potential for hepatotoxicity, will be listed. Results from any hepatic monitoring procedures, such as a magnetic resonance elastography (MRE) scan, and biopsy assessments will be listed, if performed.

Hepatic risk factor assessment data will be listed. Liver related signs and symptoms data will be summarized by treatment, if there are sufficient data available, and listed. Alcohol and recreational drug use data will also be listed.

All hepatic chemistry, hematology, coagulation, and serology data will be listed. Values outside the reference ranges will be flagged on the individual participant data listings.

#### **10.4.9 Immunogenicity Assessments**

Immunogenicity data may be listed and frequency tables may be presented if analysed. The frequency and percentage of participants with pre-existing antidrug antibody (ADA) and with treatment-emergent ADAs (TE ADAs) may be presented. TE ADAs are those that are boosted or induced by exposure to study drug, with a 4-fold increase in titer compared to baseline if ADAs were detected at baseline or a titer 2-fold greater than the minimum required dilution (1:10) if no ADAs were detected at baseline, where baseline is defined as Day 1 predose.

Venus blood samples will be stored for future analysis to determine antibody production against LY3493269. Any analysis, whether performed at a later date or during this study, will be performed by Eli Lilly. If applicable, the frequency and percentage of participants with cross-reactive binding to native GIP, GLP-1 or neutralizing antibodies, if measured, may also be tabulated for participants with TE ADA.

The relationship between the presence of antibodies and PK parameters of LY3493269 may be assessed if deemed appropriate.

#### **10.4.10 Hypersensitivity reactions**

For all drug hypersensitivity reactions that occur, additional follow-up data will be collected to assess the participant's medical history, alternative causes, and symptoms.

These data will be listed.

#### **10.4.11 Elevated Lipase or Amylase**

If a patient experiences elevated serum amylase or lipase values  $\geq 3 \times$  ULN, additional monitoring and tests may be performed to confirm the abnormality.

The frequency of serum amylase or lipase values  $\geq 3 \times$  ULN will be summarized by treatment and listed.

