### **8.2.4.      Clinical Safety Laboratory Tests**

See Appendix 2 for the list of clinical laboratory tests to be performed and the SoA for the timing and frequency.

The investigator must review the laboratory results, document this review, and report any clinically relevant changes occurring during the study as an AE. The laboratory results must be retained with source documents unless a Source Document Agreement or comparable document cites an electronic location that accommodates the expected retention duration. Clinically significant abnormal laboratory findings are those that are not associated with the underlying disease, unless judged by the investigator to be more severe than expected for the participant's condition.

All laboratory tests with values considered clinically significantly abnormal during participation in the study or within 28 days after the last dose of study intervention should be repeated until the values return to normal or baseline or are no longer considered clinically significant by the investigator or medical monitor.

- If such values do not return to normal/baseline within a period of time judged reasonable by the investigator, the etiology should be identified and the sponsor notified.
- All protocol-required laboratory assessments, as defined in Appendix 2, must be conducted in accordance with the SoA, standard collection requirements, and applicable laboratory manual.

If laboratory values from nonprotocol-specified laboratory assessments performed at an investigator-designated local laboratory require a change in participant management or are considered clinically significant by the investigator (for example, SAE or AE or dose modification), then report the information as an AE.

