### **Asymptomatic elevation of serum amylase and/or lipase**

Serial measures of pancreatic enzyme levels have limited clinical value for predicting episodes of acute pancreatitis in asymptomatic patients (Nauck 2016; Steinberg et al. 2017ab). Therefore, further diagnostic follow-up of cases of asymptomatic elevation of pancreatic enzymes (lipase and/or p-amylase  $\geq 3$  x ULN) is not mandated but may be performed based on the investigator's clinical judgment and assessment of the participant's overall clinical condition.

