## 10.7. Appendix 7: Pancreatic Monitoring

GLP-1 agonists have been associated with a possible risk of acute pancreatitis. In 2006, the United States prescribing information for exenatide was revised to include the event of pancreatitis. In 2007, the US prescribing information for this medication was amended to include pancreatitis under “Precautions.” Epidemiologic studies have indicated that there is an increased incidence and prevalence of pancreatitis in persons with T2DM.

To enhance understanding of the natural variability of pancreatic enzymes in the T2DM population and, to assess for any potential effects of LY3493269 on the exocrine pancreas, amylase and lipase values will be monitored in all current and future clinical trials with LY3493269.

Additional monitoring will be requested for amylase or lipase values  $\geq 3x$  the ULN at any visit after randomization. Lipase and amylase values may also be obtained at any time during the clinical trials for any participant suspected of having symptoms suggestive of pancreatitis (such as severe GI signs and/or symptoms), at the investigator’s discretion.

Acute pancreatitis is an AE defined as an acute inflammatory process of the pancreas that may also involve peripancreatic tissues and/or remote organ systems. The diagnosis of acute pancreatitis requires 2 of the following 3 features:

- abdominal pain characteristic of acute pancreatitis
- serum amylase and/or lipase  $>3x$  ULN, and
- characteristic findings of acute pancreatitis on CT scan or magnetic resonance imaging.

Most participants with acute pancreatitis experience abdominal pain that is located generally in the epigastrium and radiates to the back in approximately one-half of the cases. The pain is often associated with nausea and vomiting.

Participants diagnosed with pancreatitis will be discontinued from the study. Investigators will be responsible for following, through an appropriate health care option, these pancreatitis AEs until the events resolve or are explained. AEs that meet the diagnostic criteria of acute pancreatitis will be captured as SAEs. For all other pancreatic AEs (such as idiopathic or asymptomatic pancreatic enzyme abnormalities), the investigator will be responsible for determining the seriousness of the event (AE or SAE) and the relatedness of the event to IP.

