## **10. STATISTICAL METHODOLOGY**

### **10.1 General**

Data listings will be provided for all data that is databased. Summary statistics and statistical analysis will only be presented for data where detailed in this SAP. For continuous data, summary statistics will include the arithmetic mean, arithmetic standard deviation (SD), median, minimum, maximum and number of observations; for log-normal data (e.g. the PK parameters: AUC and  $C_{\max}$ ) the geometric mean and geometric coefficient of variation (CV%) will also be presented. For categorical data, frequency count and percentages will be presented. Data listings will be provided for all participants up to the point of withdrawal, with any participants excluded from the relevant population highlighted. Summary statistics and statistical analyses will generally only be performed for participants included in the relevant analysis population. For the calculation of summary statistics and statistical analysis, unrounded data will be used.

For change from baseline summary statistics, each individual change from baseline will be calculated by subtracting the individual participant’s baseline value from the value at that time point. The individual participants’ change from baseline values will be used to calculate the summary statistics (arithmetic mean, arithmetic SD, median, minimum, maximum and number of observations) using a SAS procedure such as Proc Univariate.

Data analysis will be performed using SAS® Version 9.4 or greater.

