### **10.4 Safety and Tolerability Assessments**

#### **10.4.1 Adverse events**

Where changes in severity are recorded in the Case Report Form (CRF), each separate severity of the adverse event (AE) will be reported in the listings, only the most severe will be used in the summary tables. A pre-existing condition is defined as a condition that starts before the participant has provided written informed consent and is ongoing at consent. A non-treatment emergent AE is defined as an AE which starts after informed consent but prior to the first dose.

A treatment-emergent AE is defined as an AE which occurs postdose or which is present prior to dosing and becomes more severe postdose.

All AEs will be listed. TEAEs will be summarized by treatment, severity and relationship to the study drug. The frequency (the number of AEs, the number of participants experiencing an AE and the percentage of participants experiencing an AE) of TEAEs will be summarized by treatment, Medical Dictionary for Regulatory Activities (MedDRA) (version is documented in the Data Management Plan [DMP]) system organ class and preferred term. The summary and frequency AE tables will be presented for all causalities and those considered related to the study drug by the investigator. Any serious AEs will be listed. AEs by day of onset will be presented.

Discontinuations due to AEs will be listed.

Adverse events of special interest (AESI) are nausea, vomiting, diarrhea, skin burning sensations and related AEs. AESIs will be listed.

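### SAP 10.4.11 counts amylase and lipase values at or above 3× ULN, not participants, so one persistently elevated participant can outweigh several people each affected once

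*SAP*

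**What the plan says.** SAP 10.4.11 says that "The frequency of serum amylase or lipase values" at or above 3× ULN will be summarised by treatment and listed. It does not say whether amylase and lipase are pooled, what the denominator is, whether the Day 1 predose result counts, or whether repeat and unscheduled results enter the table. The general rule in SAP 10.1 does not settle the unit: "For categorical data, frequency count and percentages will be presented".

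Elsewhere the SAP is explicit. For adverse events (10.4.1), frequency is spelled out as "the number of AEs, the number of participants experiencing an AE and the percentage of participants experiencing an AE". For anti-drug antibodies (10.4.9), the unit is also the participant.

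On further testing after such a value, four places differ:

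- SAP 10.4.11: "additional monitoring and tests may be performed to confirm the abnormality".
- Protocol 8.2.5.2, on asymptomatic elevation: further diagnostic follow-up "is not mandated but may be performed based on the" investigator's judgment.
- Protocol Appendix 7 (10.7): "Additional monitoring will be requested for amylase or lipase values" at or above 3× ULN.
- Protocol 8.2.4: laboratory values judged clinically significantly abnormal "should be repeated until the values return to normal or baseline or are no longer considered clinically significant".

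**The concern.** Protocol Appendix 7 gives one purpose of monitoring these enzymes as assessing possible effects of the drug on the exocrine pancreas. The natural question for each arm is how many people had a marked elevation. A count of values mixes that with how long each elevation lasted, how many samples were taken and whether both enzymes rose together. Values from one person are not independent, and with about 10 people per arm a single participant can dominate the count.

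SAP 10.4.11 is the only threshold-based by-arm summary of these enzymes in the SAP. Protocol 9.3.3 would have tabulated out-of-range chemistry by treatment group. SAP 10.4.5 only lists and flags it, and the SAP states in Section 3 that it supersedes the protocol's statistical section. If the table ranks the arms wrongly, no other planned threshold table corrects it.

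**Working it through.** The plan states no figure on this point, so there is none to reproduce. The check is a direct count.

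**Inputs**

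- Scheduled post-dose laboratory visits: Days 5, 8, 15, 29 and 43, so 5 per participant (Protocol 1.3 and 10.2.1). Both enzymes are in the chemistry panel (Protocol 10.2).
- Target of 10 completers per treatment (Protocol 4.1, SAP 5). Part B is cancelled (SAP 5 and 12), so the arms are A1, A2 and A3.
- Assumption: the SAP gives no denominator, so I use all scheduled post-dose results, 10 × 5 = 50 per enzyme per arm and 100 over both.
- Assumption: how elevations are spread over people is hypothetical, so a range is shown.

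**Step 1. Most values one person can supply from scheduled visits.** One enzyme: 5 × 1 = 5. Both enzymes: 5 × 2 = 10.

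**Step 2. One enzyme, no repeats.** Arm P has one participant elevated at every visit. Arm Q has m participants elevated once each. P shows more values when 5 > m, that is, for m up to 4. With m = 4:

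| | Arm P | Arm Q |
|---|---|---|
| Values | 5/50 = 10% | 4/50 = 8% |
| Participants | 1/10 = 10% | 4/10 = 40% |

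Adding the Day 1 predose sample to the denominator gives 5/60 = 8.3% against 4/60 = 6.7%, the same order.

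**Step 3. Both enzymes pooled, no repeats.** If each affected participant in Q has one elevated value in one enzyme, P shows more values when 10 > m, so for m up to 9. With m = 6 it is 10/100 = 10% against 6/100 = 6%, while by participant it is 1/10 against 6/10. If each affected participant in Q is elevated on both enzymes at one visit, the condition is 10 > 2m, so m up to 4.

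**Step 4. One enzyme, if repeats were included.** For m of 5 or more, the elevated repeats P's participant needs beyond the 5 visits are m + 1 − 5:

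| m in arm Q | 5 | 6 | 8 | 10 |
|---|---|---|---|---|
| Repeats needed | 1 | 2 | 4 | 6 |

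With m = 6 and 2 repeats in P only, the result is 7/52 = 13.5% against 6/50 = 12.0%. If P's participant is elevated at only one scheduled visit, 6 elevated repeats are needed to pass m = 6 (1 + 6 = 7 against 6).

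**Step 5. Counting participants.** The participant figures, such as 1/10 against 4/10 or 6/10, do not change with the duration of the elevation or with further elevated results in people already counted.

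The reversal therefore arises from the scheduled visits alone. Repeats can only add to it.

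**The case against.** The strongest reply is that the sentence is ambiguous rather than wrong. In SAP 10.4.1 the word frequency covers participants as well as events, and the detailed table layout is in a shell document that is not among the documents reviewed. That shell may already count participants. This stands as far as it goes. But the 10.4.1 definition is given for adverse events only, and a programmer who follows 10.4.11 literally will count results.

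The second reply is that little depends on the table. Safety evaluation is descriptive and the safety endpoint is TEAEs. Values at or above 3× ULN are listed, so with about 30 participants the people affected can be counted by hand. Amylase and lipase are also summarised by treatment and time point under SAP 10.4.5. Clinically relevant laboratory changes are reported as adverse events, which are tabulated by participant. Participants are healthy, have enzymes no more than 1.5× ULN at entry and take three doses, so there may be few such values or none. All of this stands, and it limits the severity.

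A reader might infer something stronger: that every value at or above 3× ULN triggers repeat tests, so the arm retested longest will look worst. The documents do not support that. The SAP makes further tests optional, and Protocol 8.2.5.2 does not mandate follow-up of asymptomatic elevation. Protocol 8.2.4 reaches only values judged clinically significant. Appendix 7 comes closest, but it speaks of monitoring being requested. Nor does the SAP say that repeat results enter the table, although it does not exclude them.

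**Conclusion.** The point holds as a minor one. SAP 10.4.11 names the value as its unit, and nothing else in the SAP supplies a participant count for this threshold. On the scheduled visits alone, one participant can contribute 5 values per enzyme or 10 over both. That arm can then show more values than one with up to 4 people affected once (one enzyme), or up to 9 (both enzymes pooled, one value each).

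These are limits of what the wording allows, not forecasts. They rest on full attendance at the five visits, 10 participants per arm and a hypothetical spread of elevations. The percentages also rest on a denominator that the SAP does not state. The documents give no rate from which to judge how likely a reversal is. The change is worth making because it is cheap and follows the SAP's own practice for adverse events and antibodies.

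**What to change.** Replace the summary sentence in SAP 10.4.11 with text such as:

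> The number and percentage of participants with at least one post-dose value ≥3× ULN will be summarized by treatment, separately for amylase and lipase. The denominator is Safety population participants with at least one post-dose result for that enzyme. Scheduled and unscheduled post-dose results both count towards whether a participant met the threshold, and each participant is counted once per enzyme. All values will be listed.

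Unscheduled results need to count. Protocol 8.2.5.2 and Appendix 7 provide for enzyme tests when pancreatitis is suspected, and a rule limited to scheduled samples could drop a participant whose only value at or above 3× ULN came from such a test. A count of values can stay as a supplement if the sponsor wants it.

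Separately, the sponsor should reconcile the statements on follow-up testing in SAP 10.4.11 and Protocol 8.2.4, 8.2.5.2 and Appendix 7. Which of them should govern is a clinical matter and is not proposed here.

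The cost is a short SAP edit and a small change to one table shell. No new data are needed.

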#### **10.4.12 Other assessments**

All other safety assessments not detailed in this section will be listed but not summarized or statistically analyzed.

### **11. INTERIM ANALYSES**

No formal interim statistical analyses are planned.

#### **Data Review during the Study**

The following reviews will be the responsibility of Eli Lilly.

##### **Part A**

A review of available safety and PK data will be conducted to determine the test formulation(s) to be evaluated in Part B.

This review will include data from at least 8 participants who have completed 3 consecutive doses of the study intervention in each of the 3 planned treatment groups, and who have completed protocol assessments up to Day 8.

## **Part B**

Emerging PK data from Part A will determine the formulations to be tested as Treatments B1 and B2, as well as the conditions (fed or fasted) under which the test or reference formulations are administered. If deemed appropriate, an interim review of PK data from Treatment B1 may be conducted prior to the initiation of Treatment B2. This review will include data from at least 8 participants who have completed 3 consecutive doses of the study intervention, and who have completed protocol assessments up to Day 8.

## **12. CHANGES FROM THE PROTOCOL SPECIFIED STATISTICAL ANALYSES**

Part B of this study has been cancelled.

## **14. DATA PRESENTATION**

### **14.1 Derived Parameters**

Individual derived parameters (e.g. PK parameters) and appropriate summary statistics will be reported to three significant figures. Observed concentration data, e.g.  $C_{max}$ , should be reported as received. Observed time data, e.g.  $t_{max}$ , should be reported as received. Number of observations and percentage values should be reported as whole numbers. Median values should be treated as an observed parameter and reported to the same number of decimal places as minimum and maximum values.

### **14.2 Missing Data**

Missing data will not be displayed in listings.

### **14.3 Insufficient Data for Presentation**

Some of the TFLs may not have sufficient numbers of participants or data for presentation. If this occurs, the blank TFL shell will be presented with a message printed in the center of the table, such as, "No serious adverse events occurred for this study."

## 15. APPENDICES

### Appendix 1: Document History

Status and Version	Date of Change	Summary/Reason for Changes
Final Version 1.0	NA	NA; the first version.
Final Version 2.0	30JUN2023	
Added additional PK parameter, <math>F_{Abs}</math>, following request from Sponsor.
 
<math>AUC(0-\infty)</math> on profile day 3 added to statistical analysis following request from Sponsor.
 
Part B of the study has been cancelled – text added to Sections 5 and 12 to clarify.
 
“Labcorp Drug Development” amended to “Fortrea” throughout.

NA = not applicable

Signature Page for VV-CLIN-123648 v1.0

Approval	PPD PKPDPMx 04-Jul-2023 13:18:29 GMT+0000
Approval	PPD Statistician 04-Jul-2023 13:26:07 GMT+0000
Approval	PPD PKPDPMx 05-Jul-2023 06:48:24 GMT+0000
Approval	PPD Statistician 05-Jul-2023 17:10:22 GMT+0000

Signature Page for VV-CLIN-123648 v1.0

Approved on 05 Jul 2023 GMT
